#### 4.4 Beginning and End of Study Definition

The overall study begins when the first participant signs the ICF. The overall study ends when the last participant completes the last study-related telephone-call or visit, withdraws from the study, or is lost to follow-up (ie, the participant is unable to be contacted by the investigator).

#### **4.4.1 Clinical Criteria for Early Study Termination**

Recruitment in the study or at (a) particular study site(s) may be stopped due to insufficient compliance with the protocol, Good Clinical Practice (GCP) and/or other applicable regulatory requirements, procedure-related problems or the number of discontinuations for administrative reasons is too high.

Early study termination will be the result of the following specified criteria:

1. Incidence or severity of adverse drug reactions in this or other studies suggest a potential health hazard to participants that negatively impact the risk:benefit ratio
2. Plans to modify or discontinue the development of the study drug

Ample notification will be provided in the event of Sponsor decision to no longer supply selumetinib or pembrolizumab.

### **5 STUDY POPULATION**

Male/Female participants who are at least 18 years of age with advanced metastatic solid tumors will be enrolled in this study.

Prospective approval of protocol deviations to recruitment and enrollment criteria, also known as protocol waivers or exemptions, is not permitted.

#### **5.1 Inclusion Criteria**

To be eligible for inclusion in this study, the participant must:

1. Have a histologically or cytologically confirmed advanced or metastatic solid tumor by pathology report and have received, or been intolerant to, all treatment known to confer clinical benefit.
2. Have measurable disease by RECIST 1.1 as assessed by local site investigator/radiology. Target lesions situated in a previously irradiated area are considered measurable if progression has been demonstrated in such lesions.
3. Have a performance status of 0 or 1 on the Eastern Cooperative Oncology Group (ECOG) Performance Scale.
4. Have the ability to swallow and retain oral medication and not have any clinically significant gastrointestinal abnormalities that might alter absorption.

Examples of clinically significant gastrointestinal abnormalities: perforation, diverticulitis, duodenal resection, esophageal stenosis.

Examples of gastric surgeries that can potentially impact absorption: lap band, Roux-en Y, sleeve.

5. Demonstrate adequate organ function as defined in [Table 2](#).

Table 2 Adequate Organ Function Laboratory Values

System	Laboratory Value
Hematological	
Absolute neutrophil count	>1,500/mcL
Platelets	>100,000/mcL
Hemoglobin	>9 g/dL or >5.6 mmol/L a
Renal	
Serum creatinine or creatinine clearance (CrCl) (measured or calculated) b or Glomerular Filtration Rate (GFR) in place of CrCl	≤1.5 X ULN OR ≥30mL/min for participant with creatinine levels >1.5 X ULN
Hepatic	
Total bilirubin (serum)	≤1.5 X ULN or Direct bilirubin ≤ULN for participants with total bilirubin levels >1.5 X ULN
AST (SGOT) and ALT (SGPT)	<2.5 X ULN or ≤5 × ULN for participants with liver metastases
Coagulation	
International Normalized Ratio (INR) or Prothrombin Time (PT)	< 1.5 X ULN unless participant is receiving anticoagulant therapy
Activated Partial Thromboplastin Time (aPTT)	< 1.5 X ULN unless participant is receiving anticoagulant therapy

ALT (SGPT) = alanine aminotransferase (serum glutamic pyruvic transaminase);          AST (SGOT) = aspartate aminotransferase (serum glutamic oxaloacetic transaminase);          GFR = glomerular filtration rate; ULN = upper limit of normal.
 
a Criteria must be met without packed red blood cell (pRBC) transfusion within the prior 2 weeks.          Participants can be on stable dose of erythropoietin (≥ approximately 3 months).
 
b Creatinine clearance (CrCl) should be calculated per institutional standard. If no local guideline is available, CrCl should be calculated using the Cockcroft-Gault Method: CrCl = [(140-age) * weight (kg) * (0.85 for females only)] / (72 * serum creatinine).
 
Note: This table includes eligibility-defining laboratory value requirements for treatment; laboratory value requirements should be adapted according to local regulations and guidelines.
	

## Demographics

6. Is male or female and a minimum of 18 years of age inclusive at the time of signing the informed consent.

## Male Participants

7. Agree to use a contraception as detailed in Appendix 5 of this protocol during the treatment period and for at least 120 days after the last dose of study intervention and refrain from donating sperm during this period.

## Female Participants

8. Not be pregnant (Appendix 5) or breastfeeding, and at least 1 of the following conditions applies:

a. Not be a woman of childbearing potential (WOCBP) as defined in Appendix 5.

OR

b. A WOCBP must agree to follow the contraceptive guidance in Appendix 5 during the treatment period and for at least 120 days after the last dose of study intervention.

## Informed Consent

9. The participant (or legally acceptable representative if applicable) provides written informed consent/assent for the study. The participant may also provide consent/assent for future biomedical research. However, the participant may participate in the main study without participating in future biomedical research.

## Additional Criteria

10. Human immunodeficiency virus (HIV) infected participants must have well controlled HIV on anti-retroviral therapy (ART), defined as:

- Participants on ART must have a CD4+ T-cell count  $>350$  cells/mm^3 at the time of screening
- Participants on ART must have achieved and maintained virologic suppression defined as confirmed HIV RNA level below 50 or the lower limit of quantification (below the limit of detection) using the locally available assay at the time of screening and for at least 12 weeks prior to screening
- Participants on ART must have been on a stable regimen, without changes in drugs or dose modification, for at least 4 weeks prior to study entry (Day 1)

## 5.2 Exclusion Criteria

The participant must be excluded from the study if the participant:

## Medical Conditions

1. Has had chemotherapy, definitive radiation, or biological cancer therapy within 4 weeks (2 weeks for palliative radiation) prior to the first dose of study treatment, or has not recovered to CTCAE Grade 1 or better from any AEs that were due to cancer therapeutics administered more than 4 weeks earlier (this includes participants with previous immunomodulatory therapy with residual immune-related AEs). Participants receiving ongoing replacement hormone therapy for endocrine immune-related AEs will not be excluded from participation in this study.

2. Has clinically active central nervous system metastases and/or carcinomatous meningitis. Participants with previously-treated brain or meningeal metastases may participate and be eligible for treatment provided they are stable and asymptomatic (without evidence of progression by MRI scan of the brain separated by at least 4 weeks after treatment), have no evidence of new or enlarging brain metastases, are evaluated within 4 weeks prior to first study treatment administration, and are off immunosuppressive doses of systemic steroids at least 2 weeks prior to enrollment.
3. Has had a severe hypersensitivity reaction ( $\geq$  Grade 3) to treatment with a monoclonal antibody/component of the study treatment, and/or has a history of allergic reactions attributed to compounds of similar chemical or biologic composition to agents and/or excipients used in the study.
4. Has an active infection requiring therapy.
5. Has a history of (non-infectious) pneumonitis that required steroids or has current pneumonitis.
6. Has an active autoimmune disease that has required systemic treatment in the past 2 years (ie, with use of disease modifying agents, corticosteroids, or immunosuppressive drugs) except vitiligo or resolved childhood asthma/atopy. Replacement therapy, such as thyroxine, insulin, or physiologic corticosteroid replacement therapy for adrenal or pituitary insufficiency, is not considered a form of systemic treatment and is allowed. Use of nonsystemic steroids is permitted.
7. Has a diagnosis of immunodeficiency or is receiving systemic steroid therapy or any other form of immunosuppressive therapy within 7 days prior to allocation.
8. Participants with known Hepatitis B or C infections, or known to be positive for Hepatitis B antigen/Hepatitis B virus DNA or Hepatitis C Antibody or RNA. Active Hepatitis C is defined by a known positive Hep C Ab result and known quantitative Hepatitis C virus RNA results greater than the lower limits of detection of the assay.

Note: No testing for Hepatitis B, Hepatitis C, and HIV is required unless mandated by local health authority.

9. HIV infected participants with a history of Kaposi's sarcoma and/or Multicentric Castleman's Disease.
10. Has undergone major surgery and has not recovered adequately from any toxicity and/or complications from the intervention prior to starting study therapy.

Note: Surgery that required general anesthesia must be completed at least 2 weeks before first study intervention administration.

Note: Surgery requiring regional/epidural anesthesia must be completed at least 72 hours before first study intervention administration and participants should be recovered.

11. Has baseline peripheral neuropathy/paresthesia Grade >1.
12. Have any medical, psychiatric, cognitive, or other condition that may compromise the participant's ability to understand the participant information, give informed consent, comply with the study protocol, or complete the study, in the opinion of the treating investigator.
13. Patients with clinically significant cardiovascular disease as defined by the following:
  - a. Uncontrolled hypertension (at randomization: systolic blood pressure  $\geq 150$  mmHg or diastolic blood pressure  $\geq 95$  mmHg, despite optimal therapy)
  - b. Left ventricular ejection fraction (LVEF)  $<55\%$  measured by echocardiography (or MUGA)
  - c. Symptomatic heart failure (NYHA grade II to IV), prior or current cardiomyopathy, or severe valvular heart disease
  - d. Uncontrolled angina (Canadian Cardiovascular Society grade II to IV despite medical therapy)
  - e. Clinically significant cardiac arrhythmia and/or conduction abnormality  $\leq 6$  months prior to start of study treatment
  - f. Myocardial infarction or acute coronary syndrome  $\leq 6$  months prior to start of study treatment
  - g. Mean QT interval calculated according to the Frederica method (QTcF) interval: Male  $>450$  ms; Female  $>470$  ms
14. Have a history of thromboembolic or cerebrovascular event(s) within 6 months prior to study enrollment, including transient ischemic attack, cerebrovascular accident, deep vein thrombosis, or pulmonary embolism.
15. Have neuromuscular disorder associated with an elevated creatine kinase (eg, inflammatory myopathy, muscular dystrophy, amyotrophic lateral sclerosis, spinal muscular atrophy).
16. Have a history of, or current, retinal vein occlusion (RVO) or current risk factors for RVO (eg, uncontrolled glaucoma, ocular hypertension, history of hyperviscosity, or hypercoagulability syndromes).
17. Have retinal degenerative disease.

18. Has a history or current evidence of any condition, therapy, or laboratory abnormality that might confound the results of the study, interfere with the participant's participation for the full duration of the study, make administration of the study treatments hazardous or make it difficult to monitor adverse effects such that it is not in the best interest of the participant to participate, in the opinion of the treating investigator.
19. Has a known psychiatric or substance abuse disorder that would interfere with the participant's ability to cooperate with the requirements of the study.
20. Is pregnant or breastfeeding, or expecting to conceive or father children within the projected duration of the study.

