### **Prior/Concomitant Therapy**

21. Has received a live-virus vaccine within 28 days of planned treatment start. Seasonal flu vaccines that do not contain live virus are permitted.
22. Has received prior therapy with compounds targeting PD-1, PD-L1, PD-L2, an MEK inhibitor (eg, cobimetinib, trametinib), or an ERK inhibitor (eg, MK-8353, GCD-0994, ulixertinib).

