### **Prior/Concurrent Clinical Study Experience**

23. Is currently participating and receiving study treatment in a study of an investigational agent or has participated and received study treatment in a study of an investigational agent or has used an investigational device within 28 days of administration of selumetinib.

Note: Participants who have entered the follow-up phase of an investigational study may participate as long as it has been 4 weeks since the last dose of the previous investigational agent.

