## 6.5.2 Prohibited Concomitant Medications

Participants are prohibited from receiving the following therapies during the Screening and Treatment Phases of this study:

- Antineoplastic systemic chemotherapy or biological therapy
- Immunotherapy not specified in this protocol
- Chemotherapy not specified in this protocol
- Investigational agents other than selumetinib (MK 5618) and pembrolizumab (MK-3475).
- For agents that may affect the metabolism of selumetinib (eg, strong inhibitors and inducers of CYP2C19 or CYP3A4), caution should be taken. However, changes in exposure of selumetinib with strong inhibitors/inducers would be moderate based on clinical evidence (1.5-fold).
- Participants should not take any supplemental vitamin E. High doses of vitamin E have been reported to cause bleeding and interrupt blood coagulation processes.

Note: Selumetinib capsules contain vitamin E in the form of D-a-tocopheryl polyethylene glycol 1000 succinate (TPGS), a water-soluble form of vitamin E, which acts as a formulation excipient.

- Radiation therapy

Note: Radiation therapy to a symptomatic solitary lesion or to the brain may be allowed at the investigator's discretion after the DLT observation period.

- Live vaccines within 28 days prior to the first dose of study intervention and while participating in the study. Examples of live vaccines include, but are not limited to the following: measles, mumps, rubella, varicella/zoster, yellow fever, rabies, Bacillus Calmette–Guérin, and typhoid vaccine. Seasonal influenza vaccines for injection are generally killed virus vaccines and are allowed; however, intranasal influenza vaccines (eg, FluMist®) are live attenuated vaccines and are not allowed.
- Systemic glucocorticoids for any purpose other than to modulate symptoms from an AE of suspected immunologic etiology. The use of physiologic doses of corticosteroids may be approved after consultation with the Sponsor.

Participants who, in the assessment by the investigator, require the use of any of the aforementioned treatments for clinical management should be removed from the study. Participants may receive other medications that the investigator deems to be medically necessary.

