## **6.6 Dose Modification (Escalation/Titration/Other)**

### **6.6.1 Dose Modifications Due to Adverse Events**

In previous studies of selumetinib and pembrolizumab monotherapy, overlapping toxicities have been observed for selumetinib and pembrolizumab (refer to IBs). These overlapping toxicities include pneumonitis, diarrhea/colitis, cardiac function decrease, and skin rash.

In the current study, the relationship of these AEs to selumetinib and/or pembrolizumab may be difficult to unambiguously assign. Therefore, if a participant experiences an AE related to either treatment, both selumetinib and pembrolizumab will be modified or discontinued as described in [Table 4](#) and [Table 5](#).

If 2 different therapies are proposed in these tables, the most conservative/effective treatment should be chosen (ie, steroid). Further, if the investigator believes the treatment emergent toxicity is unambiguously related to only one of the agents, they may continue the participant on the unrelated agent following consultation with the Sponsor.

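### Exclusion 1 requires toxicity recovery only for therapy given more than 4 weeks earlier, so Grade 2 toxicity from permitted or unaddressed recent therapy can enter the DLT window

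*Combined protocol and SAP*

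**What the plan says.** Exclusion 1 in Section 5.2 has two halves. The washout half reads "Has had chemotherapy, definitive radiation, or biological cancer therapy within 4 weeks (2 weeks for palliative radiation) prior to the first dose of study treatment". The recovery half excludes a participant who "has not recovered to CTCAE Grade 1 or better from any AEs that were due to cancer therapeutics administered more than 4 weeks earlier", with an exception for ongoing hormone replacement after endocrine immune-related events.

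Three other provisions bear on recent therapy:

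- Exclusion 22 applies whatever the interval: "Has received prior therapy with compounds targeting PD-1, PD-L1, PD-L2, an MEK inhibitor (eg, cobimetinib, trametinib), or an ERK inhibitor".
- Exclusion 23 covers investigational products only; its time limit appears in the words "has used an investigational device within 28 days of administration of selumetinib", and a note asks for 4 weeks since the last investigational dose.
- Section 6.5.2 lists therapies barred during screening and treatment. It begins with "Antineoplastic systemic chemotherapy or biological therapy" and goes on to immunotherapy, investigational agents and radiation. It does not name approved targeted or hormonal anticancer drugs.

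Inclusion 1 requires participants to "have received, or been intolerant to, all treatment known to confer clinical benefit". Section 6.6.2.2 counts listed toxicities in the first 21 days as DLTs if the investigator rates them at least possibly related. Its item 9 makes missing more than 25% of selumetinib doses in the first cycle because of drug-related AEs a DLT, with no grade threshold.

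**The concern.** A recovery rule should ensure that toxicity seen in the DLT window starts from a clean baseline. Here it reaches only older therapy. Where recent therapy is allowed, or not mentioned, a participant can start with a Grade 2 toxicity that would have excluded them had the causative therapy been older.

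This bears on the primary endpoint. Section 6.6.1 says of the two study drugs: "These overlapping toxicities include pneumonitis, diarrhea/colitis, cardiac function decrease, and skin rash". Rash and diarrhea from a previous agent can therefore look like toxicity of the combination. The examples of unrelated causes in Section 6.6.2.2 (progression, environment, trauma) do not mention earlier anticancer therapy, and the definition has no general rule for toxicity present at baseline. A misattributed event enters Table 1 at the current selumetinib dose and pushes the decision toward staying or de-escalating, and so toward a lower preliminary RP2D.

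**Working it through.** **Step 1. Which recent therapies fall between the two halves?** The table takes a Grade 2 non-laboratory toxicity from therapy given within 4 weeks of first dose.

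| Last therapy | Excluded by washout or other criterion? | Covered by recovery half? |
|---|---|---|
| Chemotherapy, biological therapy, definitive radiation | Yes, exclusion 1 | Not needed |
| PD-1/PD-L1/PD-L2, MEK or ERK agents | Yes, exclusion 22 | Not needed |
| Investigational agents | Yes, exclusion 23 | Not needed |
| Palliative radiation, days 15 to 28 | No, allowed after 2 weeks | No |
| Approved small-molecule targeted or hormonal agents | Not named | No |

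The gap is the last two rows. The last row closes if chemotherapy is read to include these agents, but the protocol does not define the word. The radiation row does not depend on that reading.

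**Step 2. How could such a toxicity become a DLT?**

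- *Worsening.* Grade 3 non-laboratory toxicity is a DLT under item 3, subject to its exceptions for some Grade 3 rash and short-lived diarrhea.
- *Missed doses.* BID dosing for 14 days gives 2 × 14 = 28 doses. 25% of 28 is 7, so 8 missed doses (4 days) meets item 9. Table 4 interrupts selumetinib for complicated Grade 1 to 2 diarrhea, and for Grade 2 rash that has worsened or not improved at reassessment within two weeks. Grade 3 is not needed.

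In the second route attribution is decisive. If the event is judged drug-related, item 9 makes it a DLT. If not, and there is no other DLT, the participant has received less than 75% of selumetinib and is replaced under Section 5.6.

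**Step 3. Reproduce Table 1.** With x DLTs in n participants the posterior is Beta(1+x, 1+n−x). For the intervals (0, 0.27), (0.27, 0.33) and (0.33, 1), the unit probability mass is posterior probability divided by interval length, and the largest gives E, S or D. DU applies if P(p > 0.30) exceeds 0.95; that cut-off is my assumption, as the documents do not state it. For n = 3:

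| x | E | S | D | P(p > 0.30) | Decision |
|---|---|---|---|---|---|
| 0 | 2.65 | 1.37 | 0.30 | 0.240 | E |
| 1 | 1.10 | 1.76 | 0.89 | 0.652 | S |
| 2 | 0.23 | 0.76 | 1.33 | 0.916 | D |
| 3 | 0.02 | 0.11 | 1.47 | 0.992 | DU |

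All 78 legible cells in rows 0 to 6 (n = 3 to 14) match. One added event moves 0/3 from E to S, 1/3 from S to D, and 2/3 from D to DU.

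**Step 4. Illustration only.** Let p be the true DLT rate of the combination and q the share of participants with a carried-over event counted as a DLT. Neither is in the documents. Taking the two as independent, the observed rate is r = 1 − (1−p)(1−q). For three participants, P(E) = (1−r)³ and P(D or DU) = 3r²(1−r) + r³. With p = 20%:

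| q | r | P(E) | P(D or DU) |
|---|---|---|---|
| 0 | 0.20 | 51.2% | 10.4% |
| 5% | 0.24 | 43.9% | 14.5% |
| 10% | 0.28 | 37.3% | 19.1% |
| 15% | 0.32 | 31.4% | 24.2% |

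From q = 0 to q = 15%, P(E) falls from 72.9% to 44.8% at p = 10%, and from 34.3% to 21.1% at p = 30%. This shows direction and sensitivity; it does not estimate what will happen in this trial.

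**The case against.** A reader might infer that any fresh toxicity gets in and is then scored as a DLT. The documents do not support that.

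- *Entry.* For chemotherapy, biological therapy and definitive radiation the two halves of exclusion 1 fit together, so the recovery clause is not wrong in general. Current pneumonitis excludes (exclusion 5), as does LVEF below 55% (exclusion 13b), and the LVEF-decrease DLT is measured against baseline. Those two overlapping toxicities give no support here. Table 2 laboratory limits are checked within 3 days of dosing, and neuropathy above Grade 1 excludes.
- *Counting.* Under Section 10.3.1, a pre-existing condition that does not worsen is not an AE. Section 8.3.1.1 records abnormal screening findings as medical history. Read strictly, both routes in Step 2 therefore need some exacerbation. Section 10.3.4 directs the investigator to weigh other drugs as a cause, and Section 6.6.2.2 excludes clearly unrelated toxicity.
- *Frequency.* Inclusion 1 makes recent targeted therapy plausible, but nothing shows how common it is. The approved kinase inhibitors mentioned in the introduction appear as study background, not as expected prior therapy. Nor do the documents show any carry-over effect on PK.
- *Catch-all.* Exclusion 18 bars therapy that might confound the results.

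Most of this stands and narrows the point. It leaves non-laboratory Grade 2 toxicity such as rash or diarrhea uncovered by a stated rule. Exclusion 18 rests on the treating investigator's opinion and does not standardize entry across sites. Worsening of an existing rash or diarrhea on a drug expected to cause both is exactly where a rating of possibly related is likely to be given.

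**Conclusion.** The point holds as a limited gap in the entry rule. Participants with unresolved Grade 2 non-laboratory toxicity are not excluded by exclusion 1 if it came from palliative radiation 15 to 28 days earlier, or from approved small-molecule or hormonal agents within 4 weeks. The second case assumes that chemotherapy does not include those agents. Such toxicity may be counted as a DLT; it is not counted automatically.

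The direction of any bias is toward staying or de-escalating. In a cohort of three, one event is enough to change the decision. The overall size cannot be determined, because the share of participants affected is not given; the percentages in the working rest on assumed rates. Table 1 itself is sound and no stated figure changes. The case for acting is that the change is small and protects the primary endpoint.

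**What to change.** In exclusion 1, remove the time qualifier from the recovery half, so that the existing Grade 1 requirement applies to AEs from any prior anticancer therapy regardless of when it was given. Keep the endocrine-replacement exception. For classes already excluded within 4 weeks this alters nothing; it takes effect only in the gap.

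Separately, reconcile exclusion 1, exclusion 23 and Section 6.5.2 so that they state which drug classes the washout covers, including whether chemotherapy takes in approved targeted and hormonal agents. Any interval is for the sponsor to set; the documents give no basis for choosing one here.

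The cost is a short wording amendment, with a few participants delayed until they recover, or excluded.
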